2.6.2 Statistical hypothesis, model, and method of analysis

No formal hypothesis testing will be conducted for the DoR analysis. The key secondary efficacy variable, DoR will be analyzed at the interim analyses for the selection phase, and the primary analysis for the expansion phase, based on the data observed in the FAS up-to the cut-off date, according to the treatment group and stratification assigned at randomization. The survival distribution of DoR will be estimated using the Kaplan-Meier method **from a**

combined pool of part 1 and part 2 data for any given arm. The results will be plotted graphically by treatment arm. The median 25th and 75th percentiles of DoR along with 95% confidence intervals will be presented by treatment group. The survival probabilities at 4, 6, 8 and 12 months, and the associated 95% confidence intervals will be summarized by treatment arm.

2.6.3 Handling of missing values/censoring/discontinuations

DoR will be censored at the date of the last adequate tumor assessment if no DoR event is observed prior to the analysis cut-off date or before the start of the new anticancer therapy date, whichever is earlier.

The date of last adequate tumor assessment is the date of the last tumor assessment with overall lesion response of CR, PR or SD before an event or a censoring reason occurred. In this case the last tumor evaluation date at that assessment will be used. If no post-baseline assessments are available (before an event or a censoring reason occurred) then the date of randomization/start date of treatment will be used.

In particular, DoR will be censored at the last adequate tumor assessment if one of the following occurs: absence of event; the event occurred after two or more missing tumor assessments; before the start of the new anti-cancer therapy. The term “missing adequate tumor assessment” is defined as a tumor assessment (TA) not performed or tumor assessment with overall lesion response of “UNK”. The rule to determine number of missing TAs is based on the time interval between the date of last adequate tumor assessment and the date of an event. If the interval is greater than twice the protocol-specified interval between the TAs and 2 times the protocol-allowed time window around assessments, then the number of missing assessments will be 2 or more.

Refer to [Table 2-13](#) for censoring and event date options and outcomes for DoR and PFS analysis (PFS analysis is further discussed in [Section 2-7](#)).

Table 2-13 Outcome and event/censor dates for DoR and PFS analysis

[figure not shown]
Situation	Date	Outcome
No baseline assessment	Date of randomization	Censored
Progression or death at or before next scheduled Assessment	Date of progression (or death)	Progressed
Progression or death after exactly one missing assessment	Date of progression (or death)	Progressed
Progression or death after two or more missing assessments	Date of last adequate assessment prior to missed assessment	Censored
No progression (or death)	Date of last adequate assessment	Censored
Treatment discontinuation due to 'Disease progression' without documented progression, i.e. clinical progression based on investigator claim	Date of last adequate assessment	Censored

Situation	Date	Outcome
New anticancer therapy given prior to protocol defined progression (including patients who crossover from the control to the treatment arm.)	Date of last adequate assessment on or prior to starting new anti-cancer therapy (or crossover treatment)	Censored
Death before first PD assessment	Date of death	Progressed

2.7 Analysis of secondary [REDACTED] efficacy objective(s)

The other secondary [REDACTED] efficacy objectives are to:

- Evaluate the efficacy of each combination arm, as measured by progression-free survival (PFS)
- Evaluate the efficacy of each combination arm, as measured by disease control rate (DCR)
- Evaluate the overall survival (OS) of each combination arm

2.7.1 Secondary [REDACTED] efficacy endpoints

Progression-Free Survival (PFS)

PFS is defined as the time from the date of randomization to the date of the first documented progression or death due to any cause. PFS will be based on both local investigator and central assessments of tumor assessments and using RECIST 1.1 criteria (see Appendix 2 of the protocol). The primary analysis will be based on FAS and will include all data observed up-to the cut-off date. PFS will be censored at the date of the last adequate tumor assessment if no PFS event is observed prior to the analysis cut-off date or before the start of the new anticancer therapy date, whichever is earlier. (See [Table 2-4 Subject Table 2-13](#) and [Section 2.7.3](#) for additional details regarding censoring rules and determination of date of last adequate tumor assessment). Discontinuation due to disease progression (collected on the ‘End of treatment’ and ‘End of post treatment follow up’ disposition pages) without supporting objective evidence satisfying progression criteria per RECIST 1.1 will not be considered disease progression for PFS derivation. Clinical deterioration will not be considered as a qualifying event for progression.

[figure not shown]
Disease Control Rate (DCR)

DCR is defined as the proportion of patients with a best overall response (BOR) of confirmed CR or PR, or SD lasting 12 weeks or longer, according to RECIST 1.1 criteria. A patient will be considered to have SD for 12 weeks or longer if a SD response is recorded at 11 weeks or later from randomization, allowing for the ± 1 week visit window for tumor assessments. DCR will be calculated using the FAS based on both the local investigator and central tumor assessments.

Overall Survival (OS)

Overall Survival (OS) is defined as the time from date of randomization to date of death due to any cause. A cut-off date will be established for each analysis of OS. All deaths occurring on or before the cut-off date in the FAS will be used in the OS analysis.

If a patient is not known to have died at the time of analysis cut-off, OS will be censored at the date of last contact.

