2.5.4 Supportive analyses

As a supportive analysis, ORR based on RECIST v1.1 criteria as per blinded independent central review (BICR) will be analyzed with the same analysis conventions as the primary efficacy analysis, and the treatment effect will be summarized by the ORR with its 95% confidence interval using the Clopper-Pearson method.

Subgroup analyses for the primary endpoint

The primary endpoint of ORR will be summarized for the subgroups specified in [Section 2.2.1](#) based on the primary analysis source (i.e., investigator assessment) and the same conventions as for the primary analysis. For each of the subgroups, the proportion of patients with objective response will be analyzed.

Forest plot (n, odds ratio, 95% CI) will be produced to graphically depict the treatment effect estimates in different subgroups. No inferential statistics (p-values) will be produced for the subgroups.

Concordance analysis of BOR

An assessment of the concordance between BIRC assessment and local assessment of the Best Overall Response for each subject will be provided by treatment arm. The calculation will be based on the percent agreement (the proportion of response outcomes that agree or match across both Independent Reviewer and Investigator Assessments):

$$\text{Percent Agreement} = \frac{\text{Number of matched responders} + \text{Number of matched non - responders}}{\text{Total Numbers of subjects assessed}}$$

Reasons for “Unknown” BOR

Patients with ‘unknown’ BOR will be summarized by reason for having unknown status. The following reasons will be used:

- No valid post-baseline assessment
- All post-baseline assessments have overall lesion response UNK
- New anti-neoplastic therapy started before first post-baseline assessment
- SD or non-CR/non-PD too early
- PD too late

Note 1: A SD or Non-CR/Non-PD is considered as “SD too early” if the SD or Non-CR/Non-PD is documented within first 11 weeks (takes into account the 1 week window for post-baseline assessments) after randomization date.

Note 2: A PD is considered as “PD too late” if the first documentation of PD is recorded more than 13 weeks after randomization date (takes into account the 1 week window for post-baseline assessments) with no qualifying CR, PR or SD or Non-CR/Non-PD in between.

Note 3: Special (and rare) cases where BOR is “unknown” due to both too early SD and too late PD will be classified as “SD too early”.

Waterfall plot to depict anti-tumor activity

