2.7.3 Handling of missing values/censoring/discontinuations

Progression-Free Survival

The date of last adequate tumor assessment is the date of the last tumor assessment with overall lesion response of CR, PR or SD before an event or a censoring reason occurred. In this case the last tumor evaluation date at that assessment will be used. If no post-baseline assessments are available (before an event or a censoring reason occurred) then the date of randomization/start date of treatment will be used.

In particular, PFS will be censored at the last adequate tumor assessment if one of the following occurs: absence of event; the event occurred after a new anticancer therapy is administered; the event occurred after two or more missing tumor assessments. The term “missing adequate tumor assessment” is defined as a tumor assessment (TA) not performed or tumor assessment with overall lesion response of “UNK”. The rule to determine number of missing TAs is based on the time interval between the date of last adequate tumor assessment and the date of an event. If the interval is greater than twice the protocol-specified interval between the TAs and 2 times the protocol-allowed time window around assessments, then the number of missing assessments will be 2 or more.

Refer to [Table 2-13](#) for censoring and event date options and outcomes for PFS.

Overall Survival

If a patient is not known to have died at the time of analysis cut-off, then OS will be censored at the date of last known date patient was alive, i.e., last contact date (see [Section 2.4](#)).

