2.5.1 Primary endpoint

Confirmed ORR is defined as the proportion of subjects with confirmed best overall response (BOR) of complete response (CR) or partial response (PR) according to RECIST 1.1.

Of note, BOR of SD will be assigned if at least one SD assessment (or better) occurred > 11 weeks after randomization (and not qualifying for CR or PR).

Tumor assessments performed after the start of any further antineoplastic therapy (i.e. any additional secondary antineoplastic therapy, radiotherapy or surgery, including limited-field palliative radiotherapy) will not be considered in the assessment of BOR. Further antineoplastic therapies will be identified via protocol deviations and from the data collected on “antineoplastic therapies since discontinuation of study treatment” (e)CRF pages. Of note, “biopsy” will not be considered as a new antineoplastic surgery.

For additional information on the primary endpoint, see the main SAP for the randomized part of the study.

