2.7.1 Secondary [REDACTED] efficacy endpoints

For secondary endpoints definition, see the main SAP for the randomized part of the study.

Note, due to small sample size at 1st interim analysis, only listings for the following secondary endpoints PFS and OS will be provided. Full analyses using Kaplan Meier method will be performed at 2nd interim analysis, primary and final analyses.

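### As written, the disease control rule credits stable disease only through a recorded SD, omitting unconfirmed CR/PR with no later SD and Non-CR/Non-PD; the PFS rule for the last adequate scan also omits Non-CR/Non-PD

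*SAP*

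**What the plan says.** **Disease control.** Main SAP 2.7.1 defines DCR as the proportion with a best overall response "of confirmed CR or PR, or SD lasting 12 weeks or longer, according to RECIST 1.1 criteria". It then gives one working test for the SD part: "A patient will be considered to have SD for 12 weeks or longer if a SD response is recorded at 11 weeks or later", counted from randomization and allowing for the one-week scan window. DCR is reported by local and by central review.

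**Stable disease elsewhere.** Arm 1A SAP 2.5.1 is wider: "BOR of SD will be assigned if at least one SD assessment (or better) occurred > 11 weeks after randomization". Main SAP 2.5.4 sets the early-SD reason for an unknown BOR by the words "A SD or Non-CR/Non-PD is considered as “SD too early” if the SD or Non-CR/Non-PD is documented within first 11 weeks". For late progression it lists the readings that would have rescued the BOR: "with no qualifying CR, PR or SD or Non-CR/Non-PD in between".

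**Arm 1A disease control.** Arm 1A SAP 2.7.1 does not carry its wider wording over to DCR: "For secondary endpoints definition, see the main SAP for the randomized part of the study".

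**PFS and DoR.** Main SAP 2.7.3, like 2.6.3 for DoR, defines the last adequate assessment as "the date of the last tumor assessment with overall lesion response of CR, PR or SD before an event or a censoring reason occurred". A missing assessment is one not done or read as unknown. The number of missing assessments, however, is derived from the time between the last adequate assessment and the event. The limit is twice the scan interval plus twice the scan window.

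**The concern.** A programmer would code the sentence in 2.7.1 as it stands. A tumour that shrank enough for PR at week 12 but progressed before confirmation would then score below one that only stayed stable and progressed at the same time. In Arm 1A the same patient could have a BOR of SD under 2.5.1 and still fail DCR under the inherited rule. Patients followed by Non-CR/Non-PD readings could never be credited with disease control through lack of progression.

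The adequate-assessment rule has the same gap. Non-CR/Non-PD is neither adequate nor missing by definition, yet the interval count passes over it. A progression that was properly followed up could therefore be censored.

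At stake are the consistency and size of two reported secondary endpoints, DCR and PFS.

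**Working it through.** The SAP states no DCR figure, so there is none to reproduce. The check applies the rules to example scan sequences and then sizes the effect.

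**1. Disease control.** Scans are placed at weeks 12 and 20. Week 12 is inferred from the 12-week rule with its one-week window in 2.7.1. Week 20 comes from main SAP 2.14, which equates 20 weeks of treatment with two post-baseline assessments.

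| Week 12, week 20 | Main 2.7.1, literal | SD or better (Arm 1A 2.5.1) | SD or better, plus Non-CR/Non-PD (as grouped in main 2.5.4) |
|---|---|---|---|
| SD, PD | controlled | controlled | controlled |
| PR, PD | **not** | controlled | controlled |
| CR, no further scan | **not** | controlled | controlled |
| PR, SD | controlled | controlled | controlled |
| PR, PR (confirmed) | controlled | controlled | controlled |
| Non-CR/Non-PD, PD | **not** | **not** | controlled |
| Non-CR/Non-PD twice | **not** | **not** | controlled |

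The first two rows show the inversion. The fourth shows that an unconfirmed PR followed by a recorded SD is not lost.

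**2. Size.** Each reclassified patient moves DCR by 1/N. The values of N are 24 and 74 (example in main SAP 2.5.2), 45 (part 1 maximum per arm, main SAP 1.1.1) and 100 (Arm 1A total).

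- 1/24 = 4.2 points
- 1/45 = 2.2 points
- 1/74 = 1.4 points
- 1/100 = 1.0 point

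The number reclassified, k, is unknown. For k from 0 to 7 of 74 the shift runs from 0 to 7/74 = 9.5 points. As an illustration, assume 26 of 74 are controlled on the literal rule (exact 95% CI):

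- k = 0: 26/74 = 35.1% (24.4, 47.1)
- k = 2: 28/74 = 37.8% (26.8, 49.9)
- k = 4: 30/74 = 40.5% (29.3, 52.6)

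**3. PFS interval count.** Assume Non-CR/Non-PD at weeks 12 and 20 and PD at week 28, with no scan read CR, PR or SD. The scan interval is not in the SAP, so two values are tried with a one-week window.

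- 8 weeks (20 − 12): limit 2×8 + 2×1 = 18 weeks
- 12 weeks: limit 2×12 + 2×1 = 26 weeks

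If the count starts at randomization, the gap is 28 weeks. It exceeds both limits, so the PD is treated as following two or more missing scans and is censored. If Non-CR/Non-PD counted as adequate, the gap would be 28 − 20 = 8 weeks and the PD would be an event. Starting at randomization is itself an assumption: 2.7.3 gives that fallback only when there are no post-baseline assessments, which is not so here. The censoring date is therefore not clearly stated.

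**4. The 11-week cut.** Main 2.7.1 includes a scan at exactly 11 weeks and Arm 1A 2.5.1 excludes it. Main 2.5.4 can be read either way. Only scans on that one day are affected.

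**The case against.** The strongest reply is that DCR rests on best overall response under RECIST 1.1, whose rules the SAP leaves to a protocol appendix that is not shown. The sentence in 2.7.1 says if, not only if, and its evident purpose is timing. If BOR for PR then PD is already SD, as Arm 1A states, the patient may fall under the first sentence of the definition. This stands in part: failure follows from a literal reading and is not declared. It does not remove the point, because the sentence is the only working test given and it is narrower than its counterparts.

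It can also be said that 2.5.4 uses SD as shorthand for Non-CR/Non-PD, and that eligibility may exclude patients without target lesions. The shorthand is plausible but not stated. The main SAP does allow for such patients: it tabulates absence of target lesions (2.3) and limits waterfall plots to measurable disease at baseline (2.5.4). Whether any occur cannot be told from the documents.

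A reader might infer three stronger conclusions that the documents do not support:

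- That every patient with an unconfirmed response at week 12 is lost. PR then SD meets the rule as written.
- That PFS for Non-CR/Non-PD patients is definitely censored at randomization. The stated fallback does not cover them, and their scans are not missing under the definition in 2.7.3.
- That DCR is biased down by a known amount. No rate of unconfirmed response or of Non-CR/Non-PD is given.

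**Conclusion.** The point holds as a narrow rule that conflicts with other parts of the plan. Coded literally, main SAP 2.7.1 fails patients with an unconfirmed CR/PR at the week-12 scan and no SD recorded later, and patients with only Non-CR/Non-PD readings. Arm 1A inherits the same rule. The adequate-assessment rule in 2.6.3 and 2.7.3 leaves open how Non-CR/Non-PD scans are dated, and can lead to a progression after such scans being censored.

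The count of affected patients is unknown and may be zero, so only the effect per patient is firm. DCR and PFS carry no hypothesis test (main SAP 2.7.2). The primary ORR test and the ORR probability thresholds for futility and expansion do not use them. Severity is minor. Confidence is moderate, because the RECIST appendix and the eligibility criteria are not shown.

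**What to change.** - **Main SAP 2.7.1:** state that SD of 12 weeks or longer is met by an overall response of SD, Non-CR/Non-PD or better (including unconfirmed CR/PR) recorded at least 11 weeks after randomization (Arm 1A: first dose), before progression and before new anticancer therapy. Arm 1A then inherits the corrected rule.
- **Main SAP 2.6.3 and 2.7.3:** add Non-CR/Non-PD to the responses that define the last adequate assessment.
- **Minor alignment:** use the same 11-week cut in main SAP 2.5.4 and Arm 1A SAP 2.5.1.

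The cost is a few words of SAP text and a small change to the derivation code. No new data are needed.

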2.7.2 Statistical hypothesis, model, and method of analysis

There will be no hypothesis testing for any of the endpoints listed below.

Progression-Free Survival

The secondary efficacy variable, PFS, will be analyzed at the interim looks, the primary analysis, and the final analysis based on the data observed in the FAS up-to the cut-off date, according to the treatment group and strata assigned at randomization. The survival distribution of PFS will be estimated using the Kaplan-Meier method. The results will be plotted graphically by treatment arm. The median 25th and 75th percentile of PFS along with 95% confidence intervals will be presented by treatment group. The survival probabilities at 4, 6, 8 and 12 months, and

the associated 95% confidence intervals will be summarized by treatment arm. As a supportive analysis, PFS will also be summarized based on the BIRC review of tumor data.

Disease Control Rate

DCR will be summarized using descriptive statistics (N, %) by treatment arm along with two-sided exact binomial 95% CIs [Clopper and Pearson 1934]. As a supportive analysis, DCR will also be summarized using descriptive statistics (N, %) based on the BIRC review of tumor data.

Overall Survival

The survival distribution of OS distribution will be estimated using the Kaplan-Meier method, and Kaplan-Meier curves, medians and 95% confidence intervals [Brookmeyer and Crowley 1982] of the medians intervals along with the proportion of patients alive at 4, 6, 8 and 12 months and the associated 95% confidence intervals will be presented for each treatment group.

ECOG performance status

The ECOG PS scale ([Table 2.14](#)) will be used to assess physical health of patients, ranging from 0 (most active) to 5 (least active):

Table 2-14 **ECOG Performance Scale**

Score	Description
0	Fully active, able to carry on all pre-disease performance without restriction
1	Restricted in physically strenuous activity but ambulatory and able to carry out work of a light or sedentary nature, e.g., light house work, office work
2	Ambulatory and capable of all self-care but unable to carry out any work activities. Up and about more than 50% of waking hours
3	Capable of only limited self-care, confined to bed or chair more than 50% of waking hours
4	Completely disabled. Cannot carry on any self-care. Totally confined to bed or chair
5	Dead

Frequency counts and percentages of patients in each score category will be provided by treatment arm and time point based on the windows defined in [Section 2.1](#).

2.7.3 Handling of missing values/censoring/discontinuations

Progression-Free Survival

The date of last adequate tumor assessment is the date of the last tumor assessment with overall lesion response of CR, PR or SD before an event or a censoring reason occurred. In this case the last tumor evaluation date at that assessment will be used. If no post-baseline assessments are available (before an event or a censoring reason occurred) then the date of randomization/start date of treatment will be used.

In particular, PFS will be censored at the last adequate tumor assessment if one of the following occurs: absence of event; the event occurred after a new anticancer therapy is administered; the event occurred after two or more missing tumor assessments. The term “missing adequate tumor assessment” is defined as a tumor assessment (TA) not performed or tumor assessment with overall lesion response of “UNK”. The rule to determine number of missing TAs is based on the time interval between the date of last adequate tumor assessment and the date of an event. If the interval is greater than twice the protocol-specified interval between the TAs and 2 times the protocol-allowed time window around assessments, then the number of missing assessments will be 2 or more.

Refer to [Table 2-13](#) for censoring and event date options and outcomes for PFS.

Overall Survival

If a patient is not known to have died at the time of analysis cut-off, then OS will be censored at the date of last known date patient was alive, i.e., last contact date (see [Section 2.4](#)).

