Waterfall graphs will be used to depict the anti-tumor activity based on local and central assessment separately. These plots will display the best percentage change from baseline in the sum of diameters of all target lesions for each patient. Only patients with measurable disease at baseline will be included in the waterfall graphs. Special consideration is needed for assessments where the target lesion response is CR, PR or SD, but the appearance of a new lesion or a worsening of non-target lesions results in an overall lesion response of PD. As a conservative approach, such assessments will not be considered for display as bars in the graph, since the percentage change in the sum of diameters of target lesions reflects the non-PD target lesion response, but the overall lesion response is PD. A patient with only such assessments will be represented by a special symbol (e.g. ★) in the waterfall graph. Assessments with “unknown” target lesion response and assessments with unknown overall response will be excluded from the waterfall plots. Patients without any valid assessments will be completely excluded from the graphs.

The total number of patients displayed in the graph will be shown and this number will be used as the denominator for calculating the percentages of patients with tumor shrinkage and tumor growth. Footnote will explain the reason for excluding some patients (due to absence of any valid assessment).

All possible assessment scenarios are described in [Table 2-12](#).

Table 2-12 Inclusion/exclusion of assessments used in waterfall graph

	Criteria for inclusion/exclusion	Possible sources of contradictions
--	----------------------------------	------------------------------------

case	Target response	Overall lesion	Include in waterfall?	Non-target	New lesion?
1	CR/PR/SD	PD	Yes but as " only	PD	any
2	CR/PR/SD	PD	Yes but as " only	any	Yes
3	UNK	UNK or PD	No	any	any
4	CR/PR/SD	UNK	No	UNK	No
5	CR/PR/SD	CR/PR/SD	Yes as a bar	SD/IR	No
6	PD	PD	Yes as a bar	any	any

Percentage change from baseline in the sum of diameters of all target lesions over the time will be displayed for individual patients per combination arm.

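### The PFS censoring rule leaves Non-CR/Non-PD out of the adequate assessments, so some documented progressions are censored and some patients have no defined censoring date

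*SAP*

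**What the plan says.** Main SAP 2.7.3 defines the anchor for PFS censoring: "The date of last adequate tumor assessment is the date of the last tumor assessment with overall lesion response of CR, PR or SD". The same definition appears in 2.6.3 for DoR. A missing adequate assessment "is defined as a tumor assessment (TA) not performed or tumor assessment with overall lesion response of" UNK. Missing assessments are not counted scan by scan but inferred from elapsed time since the last adequate assessment: "If the interval is greater than twice the protocol-specified interval between the TAs and 2 times the protocol-allowed time window around assessments", two or more are taken to be missing. PFS is censored when "the event occurred after two or more missing tumor assessments". The fallback to the date of randomization or start of treatment has its own condition: "If no post-baseline assessments are available (before an event or a censoring reason occurred").

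Elsewhere the SAP uses Non-CR/Non-PD as a reading in its own right. In 2.5.4, a progression is too late for BOR only when it comes "with no qualifying CR, PR or SD or Non-CR/Non-PD in between". The SAP also allows for patients without target lesions: the waterfall plot rule in 2.5.4 says "Only patients with measurable disease at baseline will be included in the waterfall graphs", and 2.3 tabulates presence or absence of target lesions at baseline. The arm 1A SAP takes over the main SAP's censoring rules by reference in its own 2.6.3 and 2.7.3.

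**The concern.** Under the 2.7.3 wording a Non-CR/Non-PD scan is neither adequate nor missing. The missing count, however, depends only on the time since the last adequate scan. A patient who attends every scan, with Non-CR/Non-PD each time, can therefore be classed as having missed two or more.

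Two things follow for such a patient. A documented later progression can be turned into a censored record. And if the patient has no event, both the rule and Table 2-13 call for the date of a last adequate assessment that does not exist. The programmer then has to invent a date. The most likely choice is the randomization or start date, which discards progression-free time that was actually observed. Early progressions would stay in as events while later progressions and progression-free time drop out, so the Kaplan-Meier estimate would move in one direction, downward.

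**Working it through.** **Inputs.** The SAP does not print the scan schedule, so it is inferred. The 11-week and 13-week limits in 2.5.4 are a scan time minus and plus a 1-week window, which puts the first scan at week 12. Section 2.14 ties two post-baseline assessments to 20 weeks, so the second scan is at week 20, 8 weeks later. The window is 1 week (2.7.1). The protocol interval itself is not at hand, so three readings are shown.

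**Anchor.** With no adequate scan, the gap is counted from randomization or start of treatment, the only alternative date the SAP offers. This is an assumption needed to apply the rule at all.

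**Limit** = 2 x scan interval + 2 x window.

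| Reading of the interval | Limit | PD by week 18 | PD at week 20 | PD at week 28 or later |
|---|---|---|---|---|
| 8 weeks | 2 x 8 + 2 x 1 = 18 weeks (126 days) | event | censored | censored |
| 12 weeks, then 8 | 12 + 8 + 2 x 1 = 22 weeks (154 days) | event | event | censored |
| 12 weeks | 2 x 12 + 2 x 1 = 26 weeks (182 days) | event | event | censored |

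So with Non-CR/Non-PD at weeks 12 and 20 and PD at week 28, the progression is censored under every reading. If Non-CR/Non-PD counted as adequate, the gap would be 28 - 20 = 8 weeks, below all three limits, and the progression would be an event at week 28.

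**Size of the possible bias.** Let q be the proportion of patients with only Non-CR/Non-PD readings before any event (assumed; the SAP gives no figure), and take true 4-month PFS as 50% (also assumed). Suppose the fallback is extended and every affected patient who is progression-free at 4 months leaves the risk set at the start. The 4-month estimate is then 1 - 0.5/(1 - 0.5q):

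- q = 0: 50%, no shift.
- q = 5%: 1 - 0.5/0.975 = 48.7%, a shift of 1.3 points.
- q = 10%: 1 - 0.5/0.95 = 47.4%, a shift of 2.6 points.

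These are upper values. Four months is 4 x 30.4375 = 121.75 days, which is shorter than every limit. Affected patients who progress between day 121.75 and the limit (126, 154 or 182 days) remain events and are still at risk at 4 months, so the true shift is smaller, more so under the longer limits.

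**The case against.** The strongest reply is that the SAP uses SD to include Non-CR/Non-PD. Note 1 in 2.5.4 files an early Non-CR/Non-PD under the label for early SD. The assessment-date rule in 5.1.2.1 divides scans into CR/PR/SD/UNK and progression, a split that is complete only if Non-CR/Non-PD belongs with SD. On that reading the defect disappears. The reading is possible but nowhere stated, and 2.5.4 repeatedly names the two categories side by side, which tells against it. A censoring rule should not depend on which reading a programmer adopts.

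A second reply is that there may be few or no such patients. This stands as a limit on size: eligibility is in the protocol, which may require measurable disease, and the waterfall sentence gives no number. The SAP also carries some text that does not apply to this design (Table 2-13 mentions crossover, which 1.1 forbids), so mention of non-measurable disease is weak evidence of enrolment.

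A third reply is that the consequence is small. With 74 patients, the SAP's example size, the standard error of a 50% proportion is sqrt(0.25/74), about 5.8 points, so even the upper shifts are under half of it. That is fair as to random error, but this would be a systematic error that is free to remove.

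Three stronger inferences are tempting and not supported. A reader might infer that every later progression is lost; in fact a progression within the limit stays an event at its own date. A reader might infer that the SAP censors these patients at day 1; it does not say so, because the fallback applies only when there are no post-baseline assessments, and these patients have them. A reader might also expect central-review PFS to suffer most, because a central reader may select no target lesion; nothing in the SAP addresses this.

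**Conclusion.** The definition of an adequate assessment in 2.7.3 and 2.6.3 is inconsistent with the SAP's own use of Non-CR/Non-PD. For a patient with only such readings, and with the gap counted from randomization or start of treatment, a progression at week 28 or later is censored under every reading of the interval, and one at week 20 under one reading of three. Without an event, the censoring date is undefined.

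Any downward bias depends on extending the fallback and on how many such patients there are; at 4 months it is at most about 1.3 or 2.6 points for an assumed 5% or 10%. PFS is a secondary endpoint without a hypothesis test (2.7.2), and neither the ORR-based decision rules nor the primary ORR test is affected. The effect on DoR is likely small, since every patient in that analysis has a CR or PR reading and therefore an adequate date. This should be corrected before PFS is derived, but it does not threaten the trial's main conclusion.

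**What to change.** In main SAP 2.7.3 and 2.6.3, define an adequate assessment as one with an overall lesion response of CR, PR, SD or Non-CR/Non-PD. In the same two places, make the fallback date apply when there is no adequate post-baseline assessment, rather than no post-baseline assessment at all; adding the category alone would leave that gap open, for example for a patient whose scans are all UNK. In 5.1.2.1, add Non-CR/Non-PD to the readings that take the latest investigation date. Arm 1A inherits the censoring change by reference. The cost is a few words in three sections and the matching derivation code; no additional data are needed.
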